Sofosbuvir is an inhibitor of the HCV NS5B RNA-dependent RNA polymerase, which is required for viral replication. Sofosbuvir is a nucleotide prodrug that undergoes intracellular metabolism to form the pharmacologically active uridine analog triphosphate (GS-461203), which can be incorporated into HCV RNA by the NS5B polymerase and acts as a chain terminator. In a biochemical assay, GS-461203 inhibited the polymerase activity of the recombinant NS5B from HCV genotype 1b, 2a, 3a, and 4a with an IC₅₀ value ranging from 0.36 to 3.3 micromolar. GS-461203 is neither an inhibitor of human DNA and RNA polymerases nor an inhibitor of mitochondrial RNA polymerase. Sofosbuvir has a very short half-life in plasma. SOF accounts for only ~4% of the drug related material circulating in plasma. The majority (>90%) of the drug-related material in plasma is in the form of GS-331007, an inactive metabolite of sofosbuvir.

Velpatasvir is an inhibitor of the HCV NS5A protein, which is required for viral replication. Resistance selection in cell culture and cross-resistance studies indicate velpatasvir targets NS5A as its mode of action.

Clinical Studies

Clinical Studies of Sofosbuvir/Velpatasvir for the Treatment of HCV

Approximately 1035 participants have been enrolled in several multicenter, Phase 3 trials to assess the efficacy of treatment with SOF/VEL in patients with genotype 1, 2, 3, 4, 5 and 6 chronic hepatitis C virus infection.

Table 2: Study ASTRAL-1: Virologic Outcomes by HCV Genotype in SOF/VEL Treated Subjects without Cirrhosis or with Compensated Cirrhosis (12 Weeks After Treatment)

	EPCLUS 12 Weeks (N=624)							
	Total (all GTs) (N=624)	GT-1			GT-2 (N=104)	GT-4 (N=116)	GT-5 (N=35)	GT-6 (N=41)
		GT-1a (N=210)	GT-1b (N=118)	Total (N=328)				
SVR12	99% (618/624)	98% (206/210)	99% (117/118)	98% (323/328)	100% (104/104)	100% (116/116)	97% (34/35)	100% (41/41)
Outcome for Subjects without SVR								
On-Treatment Virologic Failure	0/624	0/210	0/118	0/328	0/104	0/116	0/35	0/41
Relapse ^a	<1% (2/623)	<1% (1/209)	1% (1/118)	1% (2/327)	0/104	0/116	0/35	0/41
Other ^b	1% (4/624)	1% (3/210)	0/118	1% (3/328)	0/104	0/116	3% (1/35)	0/41

GT = genotype; no subjects in the placebo group achieved SVR12.

- a. The denominator for relapse is the number of subjects with HCV RNA <LLOQ at their last on-treatment assessment
- b. Other includes subjects who did not achieve SVR and did not meet virologic failure criteria.

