A subset of women (n=5) will participate in a sub-study to determine the quantity of drugs (SOF and VEL) transferred into breastmilk. Because the drug has not been studied in infants, all expressed milk will be maintained by the study. We ask each of the 5 women to express 5 samples of breastmilk and have paired blood samples collected at their convenience. Samples will be obtained starting at least 6 hours after the first dose and no sooner than 6 hours from a previous sample. All samples will be obtained by day 10 postpartum. The time of prior SOF/VEL dosing will be carefully recorded as well as the time of the breastmilk and blood collection.

Participants will be instructed to take their daily dose at home as usual. This subsample of participants will be given a pill box (Wisepill) that tracks drug timing so that we have accurate time stamp for when the drug was taken. This is important for the PK study to ensure women were adherent with the medication and to track the time of prior doses in relation to milk and blood collection.

Women will be asked to only express milk when they are at Magee-Womens Hospital under the supervision of the study staff. Women will be asked to express until both breasts are soft and the milk expression rate slows. Because women will be pumping infrequently, their milk volume will diminish and by 10 days, will be of limited volume. Individual venipuncture(s) will be used to collect all plasma samples, and participants will be instructed on how to pump to obtain breastmilk samples.

Case report forms will be completed for each set of breastmilk and blood samples obtained. Two 5-mL breastmilk samples will be processed and stored. One 5-mL aliquot of whole intact milk will be transferred to a cryovial and stored. The second 5-mL aliquot will be centrifuged, the lipid layer removed and transferred to a cryovial and the remaining fluid transferred to a separate cryovial. All three cryovials will be stored at -80°Celcius until shipment to the Colorado Antiviral Pharmacology Laboratory for analysis. 5-mL of blood will be

obtained in a K2 EDTA tube and centrifuged, the plasma transferred to a cryovial and stored at -80°Celcius until shipment to the Colorado Antiviral Pharmacology Laboratory.

SOF, the SOF metabolite GS-331007 and VEL will be measured in plasma and breastmilk using validated LC/MS-MS methods at the Colorado Antiviral Pharmacology Laboratory.

Table 8: Breastmilk Pharmacokinetics Visits (PK1-5)

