completeness and accuracy and address any issues with data quality. Descriptive summaries will include the mean and standard deviations (or medians and quartiles for skewed distributions) for continuous variables and frequencies and proportions for categorical variables. 95% confidence intervals for means and proportions will be calculated. To visually examine distributions, boxplots and histograms will be constructed for continuous variables. Poisson regression analyses will be conducted for rates of SVR following treatment. Logistic regression analysis will be used for the remaining dichotomous outcome variables (IVDU relapse, HCV reinfection). Outcomes will be summarized overall and by race, age, parity, income, and insurance. All analyses will be conducted using STATA (StataCorp. 2013. Stata Statistical Software: Release 13. College Station, TX).

Analysis of SVR12

Approximately 98% of patients treated with SOF/VEL for 12 weeks obtained an SVR12. Therefore, we estimate that at least 29 out of the 30 chronically HCV-infected postpartum women will have a SVR12 after treatment.

Analysis of breastmilk pharmacokinetics

Drug concentrations in breastmilk and plasma will be listed and summary statistics will be used to describe the derived PK parameters. Nonlinear mixed effects modeling will be used to determine the pharmacokinetics of SOF, GS-331007, and VEL in breastmilk and plasma. The ratio of milk to plasma will be reported.

Analysis of Safety Endpoints

Rates of abnormal safety laboratory assessments will be compared to those reported in the literature on historic controls. Statistical significance will be determined by chi-square test.

Study Oversight

No Data and Safety Monitoring Board oversight is planned for this study, however, a medical monitor will provide oversight for this study. The medical monitor will be an independent physician investigator from the University of Pittsburgh who has experience monitoring clinical trials among subjects with chronic HCV infection. Reviews of study progress, including rates of participant accrual, retention, completion of primary and main secondary endpoint assessments will take place approximately every 3 months, and as needed. At the time of these reviews, or at any other time, the medical monitor may recommend that the study proceed as designed, proceed with design modifications, or be discontinued.

DATA HANDLING AND RECORDKEEPING

Data Management Responsibilities

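### The breast-milk sampling rules do not ensure that any woman is sampled in the early hours after a dose, so the sofosbuvir milk/plasma ratio and model may not be estimable

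*Combined protocol and SAP*

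**What the plan says.** Breast-milk concentrations of sofosbuvir (SOF), its metabolite GS-331007 and velpatasvir (VEL) are a secondary endpoint.

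- **Sampling** (Breastmilk Pharmacokinetics Substudy): "We ask each of the 5 women to express 5 samples of breastmilk and have paired blood samples collected at their convenience". The only timing rules are "Samples will be obtained starting at least 6 hours after the first dose and no sooner than 6 hours from a previous sample" and "All samples will be obtained by day 10 postpartum". No nominal time after a dose is set for any sample. Dose and collection times are recorded, and the subset uses a Wisepill box that time-stamps doses.
- **Where the dose is taken:** the substudy text has the daily dose taken at home. Table 8 and Appendix I list a timed dose as a procedure of the PK visits. The section on adherence counseling recommends dosing between 8 and 9 am.
- **The drug** (Mechanism of Action): "Sofosbuvir has a very short half-life in plasma". No figure is given. SOF is put at about 4% of circulating drug-related material and GS-331007 at more than 90%.
- **Analysis** (Analysis of breastmilk pharmacokinetics): "Nonlinear mixed effects modeling will be used to determine the pharmacokinetics of SOF, GS-331007, and VEL in breastmilk and plasma", and "The ratio of milk to plasma will be reported". The ratio is not defined as single-point or AUC-based, and nothing is said about values below the quantification limit.
- **Aim:** the substudy sets out to "determine the quantity of drugs (SOF and VEL) transferred into breastmilk", although the listed endpoint is a concentration.

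**The concern.** A drug with a very short half-life can be characterised only from samples taken soon after a dose. The one rule that ties a sample to a dose keeps it at least 6 hours away, and the rest is left to when a woman can attend. Whether SOF is sampled while it is measurable therefore depends on visit hours that the protocol does not set.

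If few or no samples are early, the SOF ratio has a plasma denominator near or below the assay limit, and the SOF model has little information on absorption, peak or AUC. The more serious risk is in interpretation. A report that SOF was not found in milk could be taken as reassurance about lactation when it shows only that sampling was late.

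**Working it through.** The protocol gives no precision or sample-size calculation for this substudy, so there is no figure to reproduce.

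**1. How much SOF is left at 6 hours.** Fraction remaining at time t after peak = 2^(-t / half-life). The half-life is not in the documents; 0.3 to 2 h is assumed.

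| Assumed half-life | 2 h | 4 h | 6 h |
|---|---|---|---|
| 0.3 h | 0.98% | 0.0097% | 0.0001% |
| 0.5 h | 6.25% | 0.39% | 0.024% |
| 1 h | 25% | 6.25% | 1.6% |
| 2 h | 50% | 25% | 12.5% |

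These are plasma fractions counted from the peak. A sample 6 h after the dose is somewhat less than 6 h after the peak, so the true fractions would be a little higher. The documents do not say how closely milk follows plasma.

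**2. What the rules permit.** The fastest permitted sequence is 6, 12, 18, 24 and 30 h after the first dose. With a second dose at 24 h, no sample lies strictly between 0 and 6 h after a dose. At the other extreme, if a woman's sampling starts on a later dosing day with one sample a day, all her samples could lie inside that window. The rules thus allow anything from 0 to 25 early samples out of 25.

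**3. What convenience timing might give.** Assumptions: dose uniform over 8-9 am (from the protocol's recommendation), one visit a day uniform over 9 am-5 pm (assumed), first sample on the first dosing day and so at 6 h or later. Four samples per woman can then be early.

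P(sample within w hours of the dose) = (8.5 + w - 9) / 8

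- Within 2 h: 1.5/8 = 0.1875. Expected 5 × 4 × 0.1875 = 3.75 of 25. P(a woman has none) = 0.8125^4 = 0.44, or about 2.2 of the 5 women.
- Within 4 h: 3.5/8 = 0.4375. Expected 5 × 4 × 0.4375 = 8.75 of 25. P(none) = 0.5625^4 = 0.10.

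If the first sample also falls on a later day, all five can be early. Within 2 h: 25 × 0.1875 = 4.7 of 25, with 0.8125^5 = 35% of women having none. Within 4 h: 25 × 0.4375 = 10.9 of 25, with 0.5625^5 = 6% having none.

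**4. Other visit hours.**

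- Four later samples uniform over 24 h: within 2 h, 20 × 2/24 = 1.7 of 25, with (22/24)^4 = 71% of women having none. Within 4 h, 20 × 4/24 = 3.3 of 25, with (20/24)^4 = 48% having none.
- All visits in the afternoon from 14:30: the latest dose is at 9 am, so every sample is at least 5.5 h after it. None of the 25 falls within 4 h.

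**The case against.** A reader might infer that the 6-hour rule shuts out early samples altogether and that a SOF ratio and model therefore cannot be derived. The documents do not support that.

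- The rule is tied to the first dose and is not repeated for later doses. Four samples per woman, or all five if sampling starts after a later dose, may be early.
- Under the 9 am-5 pm assumption, the chance that at least one of the 20 later samples falls within 2 h of a dose is 1 - 0.8125^20 = 98%. Complete absence of early data is not the expected outcome there.
- Dose and sample times are recorded accurately, and mixed-effects models are suited to sparse, irregular sampling. A paired ratio can be formed wherever both matrices are quantifiable.
- No half-life or assay limit is given, so it cannot be asserted that most SOF values will be below quantification.
- If the timed dose in Table 8 is given at the PK visit, samples might be taken just before or soon after it, and the home-dosing figures above would not apply.
- The short half-life is stated for SOF only. Nothing shows that GS-331007 or VEL would be poorly estimated.

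All of this stands, and it limits the point to SOF and to what is not ensured. It does not remove the point. Accurate time stamps show when a sample was taken but cannot replace early samples that were never drawn. A few early samples from two or three women are a weak basis for a SOF model in two matrices.

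The absence of any mention of expressed volume is a lesser matter. The endpoint is concentration, the case report form fields are not shown, and the protocol itself expects volume to fall with infrequent pumping.

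**Conclusion.** The concern holds for SOF: the sampling rules do not ensure an early post-dose sample in any woman, so the SOF part of the model and the SOF milk/plasma ratio may not be estimable, and a negative milk result could be an effect of timing.

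The expected number of the 25 samples within 4 h of a dose runs from none (all visits at 14:30 or later) through 3.3 (any hour) to 8.75 (9 am-5 pm). In that last case 3.75 fall within 2 h and about 44% of women have none within 2 h. These figures rest on home dosing at 8-9 am, on assumed visit hours with uniform attendance, and on the first sample being taken on the first dosing day. How much the missing early samples matter depends on the half-life: at an assumed 0.3 to 2 h, between about 0.0001% and 12.5% remains 6 h after peak.

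This is a secondary endpoint in a five-woman substudy of a pilot, but the remedy is small.

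**What to change.** 1. Keep five paired samples per woman, but assign them to post-dose windows over different days, checked against the Wisepill time stamp: at least one at about 0.5-2 h, one at 2-4 h, one later in the day and, where feasible, one just before the next dose at a morning visit. The remaining sample can stay at the woman's convenience. Do not require overnight attendance. A first-day sample under the present 6-hour rule can serve as the later-in-the-day sample.
2. Define the milk/plasma ratio as a model-based AUC ratio, and list paired concentration ratios by time after dose.
3. State that values below the quantification limit are treated as censored, and report any undetected SOF result with its time after dose.
4. If an amount transferred is to be reported, record the weight or volume of each expression. Otherwise, word the aim as concentration.
5. Reconcile at-home dosing in the substudy text with the timed dose listed for PK visits in Table 8 and Appendix I, because this determines when samples fall.

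The cost is protocol wording, possibly one case report form field, and somewhat less scheduling freedom for five participants. No extra women, samples or assays are needed. One sample a day on five separate days, ending by day 10, requires sampling to start by day 6. A woman who starts later would need two windows on one day, at least 6 h apart.

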In any of the above cases or in the case that participation in the study elicits any emotional distress, Magee-Womens Hospital social workers will be available at all times by pager. All of these social workers have received extensive training in behavioral health assessment/management, suicide intervention, and IPV and crisis management. Clinical investigators will also be available for consultation on difficult cases at all times by pager. The Women's Center and Shelter of Greater Pittsburgh's telephone hotline, supported 24 hours a day, will also be available. Although we recognize that contacting the social workers for intervention with our study participants constitutes an intervention that directly impacts the study results, our first priority is the safety and well-being of our participants. In these situations, we will first ensure the appropriate care of the participants and then account for the events when performing our analyses.

Any participants who are in immediate danger, threaten suicide, or constitute any potential harm to others will be immediately referred to social workers or behavioral medicine experts who are on call for all hospital patients. The usual protocol for social work or behavioral medicine in our institution is to communicate and collaborate with the obstetric care providers. We will thus leave the decision to contact and inform the obstetric care providers of any relevant and ongoing behavioral health concerns to the social work or behavioral medicine experts.

CLINICAL MANAGEMENT

Guidelines for clinical management and permanent discontinuation of study medication are outlined in this section. In general, the physician investigators will only discontinue study medication if they feel that the risk of study medication continuation outweighs the benefits of study medication continuation. The physician investigators will document all permanent discontinuations on applicable CRFs.

Grading System

AE severity grading is described in Section 8.3.1.

Dose Modification Instructions

No dose modifications will be permitted in this study.

General Criteria for Permanent Discontinuation of Study Medication

A participant will be permanently discontinued from medication use by the physician investigators for any of the following reasons, according the HCV treatment guidelines:

- 5-fold or greater increase in ALT or AST at the V1 or V2 compared to baseline result (screening visit), confirmed by immediate repeat testing

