- Any increase of ALT or AST of less than 5-fold from baseline (screening visit) V1 or V2 visit that is accompanied by any weakness, nausea, vomiting, or jaundice

- 3-fold or greater increase in ALT or AST accompanied by bilirubin $>2x$ the upper limit of normal, confirmed on immediate repeat testing
- HIV seroconversion occurs during the time of study medication use
- Participant is unable or unwilling to comply with required study procedures
- If the participant desires to breastfeed
- Participant might be put at undue risk to their safety and well-being by continuing medication use, according to the judgment of the study investigators. The study investigators will consult with the independent safety physician prior to all study medication discontinuation instituted for this reason.

Any time a participant is permanently discontinued from study medication (prior to completion of the 12 week course of study medication), HCV resistance testing will be performed.

Permanent Discontinuation in Response to Adverse Events

Grade 1 or 2

In general, a participant who develops a Grade 1 or 2 AE as defined by the DAIDS Table for Grading Adult and Pediatric Adverse Events, Version 1.0, December 2004 (Clarification dated August 2009) regardless of relationship to study medication will continue study medication use.

Grade 3

For participants who develop a Grade 3 AE as defined by the DAIDS Table for Grading Adult and Pediatric Adverse Events, Version 1.0, December 2004 (Clarification dated August 2009) that is judged by the study investigators to be unrelated to study medication, the study medication will continue. The study medication must be permanently discontinued for participants who develop a Grade 3 AE judged by a physician investigators to be related to the study medication.

Grade 4

If a participant develops a Grade 4 AE as defined by the DAIDS Table for Grading Adult and Pediatric Adverse Events, Version 1.0, December 2004 (Clarification dated August 2009) and the AE is determined to be related to study medication, then study medication must be permanently discontinued.

Any time a participant is permanently discontinued from study medication (prior to completion of the 12 week course of study medication), HCV resistance testing will be performed.

HIV-1 Infection

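### The symptom-based ALT/AST stop needs no repeat test but is capped below 5-fold, so the written rule asks for more evidence when a symptomatic woman's rise is larger

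*Combined protocol and SAP*

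**What the plan says.** The list under General Criteria for Permanent Discontinuation of Study Medication is mandatory, and one reason is enough: "A participant will be permanently discontinued from medication use by the physician investigators for any of the following reasons, according the HCV treatment guidelines". Three of its reasons concern liver enzymes.

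- **Bullet 1:** "5-fold or greater increase in ALT or AST at the V1 or V2 compared to baseline result (screening visit), confirmed by immediate repeat testing".
- **Bullet 2:** "Any increase of ALT or AST of less than 5-fold from baseline (screening visit) V1 or V2 visit that is accompanied by any weakness". The symptom clause in full is "accompanied by any weakness, nausea, vomiting, or jaundice". No repeat is mentioned.
- **Bullet 3:** a rise of 3-fold or more with bilirubin above twice the upper limit of normal (ULN), "confirmed on immediate repeat testing".

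Table 1 defines V1 and V2 as Screening A and Screening B.

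Treatment can also end by other routes:

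- The opening of Clinical Management says that investigators "will only discontinue study medication if they feel that the risk of study medication continuation outweighs the benefits of study medication continuation".
- Grade 3 or Grade 4 adverse events judged related to the drug require a permanent stop.
- An undue-risk bullet allows a stop on judgement, but the investigators "will consult with the independent safety physician prior to all study medication discontinuation instituted for this reason".
- Criteria for Early Termination of Study Participation lets investigators withdraw a participant to protect her safety.

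**The concern.** A stopping rule should not become harder to meet as the signal worsens. Among women with weakness, nausea, vomiting or jaundice, this one does. Below 5-fold a single result meets a mandatory criterion. At 5-fold and above the cap in bullet 2 excludes her, and each enzyme criterion that remains requires a second result.

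What is at stake is individual safety: a delay, or a repeat that fails to confirm, in the woman with the larger rise. The study's feasibility, acceptability and adherence endpoints are not in question.

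**Working it through.** **1. The three bullets as a decision table.** The visit label is taken here to mean on-treatment visits.

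| Rise from baseline | Symptoms or jaundice | Bullet that applies | Repeat needed? |
|---|---|---|---|
| Below 5-fold | Yes | 2 | No |
| 3-fold to below 5-fold, bilirubin >2x ULN | No | 3 | Yes |
| 5-fold or more | No | 1 (also 3 if bilirubin >2x ULN) | Yes |
| 5-fold or more | Yes | 1 (also 3 if bilirubin >2x ULN) | Yes |

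A jaundiced woman with a 4.9-fold rise meets bullet 2 on one draw. At 5.0-fold she needs two.

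**2. The visit label.** V1 and V2 precede treatment. If bullet 1 is literally tied to them, it cannot operate on treatment. If bullet 2 still operates (there, V1 or V2 can be read as naming the baseline), a symptomatic woman at 5-fold or more has no enzyme-mandated stop unless bilirubin is >2x ULN, and then only after a repeat. If bullet 2 is tied to V1 and V2 as well, neither bullet works on treatment. The problem is then the label, not an inversion.

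**3. What the repeat decides for a symptomatic woman**, on the reading in step 1:

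- Still 5-fold or more: bullet 1 stops her.
- Below 5-fold but above baseline, symptoms persisting: bullet 2 stops her.
- At or below baseline, or below 5-fold with symptoms gone: no enzyme stop on that result.

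The repeat changes the outcome only in the last case, which covers a bad sample or a rapidly settling picture.

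**4. Measurement noise.** Assume lognormal variation with within-person coefficient of variation CV, so sigma = sqrt(ln(1 + CV²)). The log ratio of a draw to baseline then has SD sqrt(2) × sigma. The documents give no CV, so a range is shown.

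| Assumed CV | P(ratio ≥ 5) | P(ratio > 1) |
|---|---|---|
| 10% | about 0 | 50% |
| 20% | 4.6 × 10⁻⁹ | 50% |
| 30% | 5.3 × 10⁻⁵ (0.005%) | 50% |
| 50% | 0.8% | 50% |

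The repeat is thus required where noise seldom explains the rise, and not where noise alone gives some increase half the time.

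**5. Frequency.** The Safety section of the background gives 0.2% permanent discontinuation for any adverse event among 1035 subjects. With that denominator 0.2% can only be 2 subjects: 2/1035 = 0.19%, exact 95% interval 0.02% to 0.70%.

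| Rate | Expected in 30 | P(at least one) |
|---|---|---|
| 0.2% | 30 × 0.002 = 0.06 | 1 − 0.998³⁰ = 5.8% |
| 0.70% (upper limit) | 30 × 0.00696 = 0.21 | 18.9% |
| 2% (assumed for postpartum women) | 30 × 0.02 = 0.6 | 1 − 0.98³⁰ = 45% |

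These are all-cause figures. A rise of 5-fold or more with symptoms would be only part of them.

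**The case against.** **No stop is missing, and the delay is short.** On the on-treatment reading, a confirmed 5-fold rise still ends treatment, and the repeat is to be immediate. Scheduled on-treatment chemistry is weeks apart, so one prompt repeat adds little. This stands, and it limits the size of the point. A reader might also infer that bullet 2 orders an instant stop. It does not: it sets no timing and only lacks a confirmation step.

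**Other routes can stop her without a repeat.** Laboratory findings are recorded as adverse events, so a related Grade 3 or 4 rise mandates a stop. Safety withdrawal under early termination needs no repeat, relatedness judgement or prior consultation. This stands as mitigation. But the adverse-event route depends on a relatedness judgement, the undue-risk route on consultation, and withdrawal is discretionary. None restores the mandatory, repeat-free stop that the smaller rise receives.

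**A hold during the repeat is not clearly barred.** I found no rule for a temporary hold, and the protocol says "No dose modifications will be permitted in this study". A reader might infer that dosing must continue while the repeat is awaited. That sentence does not mention a hold, so it does not support the inference.

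**The source cannot be seen.** The list is attributed to HCV treatment guidelines, and the cap may come from them. This cannot be settled from the documents, but the wording has the same effect whatever its origin.

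**A repeat could be added to bullet 2 instead.** That would also remove the inversion. Nausea was reported in 9% of treated subjects, about as often as on placebo, and the protocol warns that incomplete treatment may lead to resistance. Suppose a CV of 50%, two draws (V6 and V8) and two enzymes counted separately. Then 30 × 2 × 2 × 0.8% = 0.96 false 5-fold readings, and with nausea alone at 9%, taken as independent, about 0.09 would be symptomatic. At a CV of 30% the count is 120 × 0.000053 = 0.006 before symptoms are considered. The cost is therefore not always zero, but adding a repeat would loosen a stop the protocol already has.

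**Conclusion.** The point holds as a wrongly bounded safety criterion. With the visit label read as on-treatment visits, a symptomatic or jaundiced woman with a rise of 5-fold or more must have it confirmed before an enzyme criterion applies, while one with a smaller rise need not.

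Two stronger readings are tempting and not supported. One is that the inversion is the same however the visit label is read. Under a literal label it becomes a missing enzyme stop (unless bilirubin is raised) or disappears, depending on bullet 2. The other is that many women would be exposed or a study result affected. The only rate in the documents implies 0.06 of 30 women for all adverse-event discontinuations together. The postpartum rate and the CVs are assumptions, and the length of the delay is not given.

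The likely consequence is a short delay or a possible non-confirmation in a rare event. This is a low-priority change, worth making because it costs so little.

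**What to change.** In bullet 2, delete the four words *of less than 5-fold* and leave the rest as it is. Because any one listed reason is enough, a symptomatic rise of any size then meets the criterion without a repeat. The repeat in bullets 1 and 3 governs only women without those symptoms. No stop is loosened, and no threshold, visit or blood draw is added.

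The cost is the repeat as a guard against a spoiled or mislabelled sample in a symptomatic woman with a large rise. The protocol already forgoes that guard for every smaller symptomatic rise.

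Correct the V1 or V2 label separately, naming the on-treatment visits meant. Whether small rises without jaundice should need a minimum size or a repeat is for hepatology to decide and is not requested here.

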- Patient centered outcomes such as health related QOL will be assessed at 6, 9 and 12 months following treatment completion

Sample Size

To evaluate the primary objective, we estimate a desired sample size of 30 participants. A subset of 5 participants will participate in the PK visits. Approximately 375 OD pregnant patients receive prenatal and postpartum care at MWH each year and approximately 50% are HCV infected. Anticipating a 75% enrollment rate, 30 HCV infected pregnant patients will be available for participation following a 12 month enrollment period.

Participant Accrual and Retention

Pregnant and postpartum chronically HCV-infected women who meet the criteria outlined in Section 5 and are interested in participating, will be enrolled into this study. Once a participant is enrolled, the study staff will make every reasonable effort to retain her for the entire study period to minimize possible bias associated with loss-to-follow-up. Participant contact information will be reviewed at each follow-up visit and participants will be asked to contact study staff if their contact information changes. If a participant cannot be contacted using her primary contact information, alternative contacts will be called in order to reach the participant. A maximum of 10% loss-to-follow-up will be targeted.

Data Analysis

Validated survey instruments will be used to collect data on patient-centered outcomes such as HCV health related quality of life (QOL). Protocol-specific survey instruments will be used to record treatment side effects, medication diaries, an assessment of missed doses and pill counts. All responses to data collection materials will be transferred into a secure database. Preliminary statistical analyses will focus on data checks for

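### SVR is a once-per-woman yes/no result assigned an unspecified Poisson regression, and its forecast of at least 29 of 30 states an expected value as a minimum

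*Combined protocol and SAP*

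**What the plan says.** Under Statistical Considerations, Data Analysis, the plan says "Poisson regression analyses will be conducted for rates of SVR following treatment". The sentence after it begins "Logistic regression analysis will be used for the remaining dichotomous outcome variables (IVDU relapse, HCV reinfection". The word for what is left over implies that SVR is itself one of the dichotomous outcomes. The plan gives no variance estimator, offset, covariates or effect measure for the Poisson model. Earlier in the same paragraph it says "95% confidence intervals for means and proportions will be calculated", without naming a method.

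Under Analysis of SVR12 it says "Approximately 98% of patients treated with SOF/VEL for 12 weeks obtained an SVR12" and concludes that "we estimate that at least 29 out of the 30 chronically HCV-infected postpartum women will have a SVR12 after treatment". No interval accompanies this forecast, and no rule covers a woman without a result.

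Under Sample Size: "To evaluate the primary objective, we estimate a desired sample size of 30 participants". Under Participant Accrual and Retention: "A maximum of 10% loss-to-follow-up will be targeted". SVR is determined at one visit (V11), three months after treatment ends. Being able to determine it is one of the primary feasibility items. SVR12 itself is not a listed endpoint and has no success threshold.

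**The concern.** A Poisson model sets the variance equal to the mean. For a proportion p the variance is p(1 − p), so model-based Poisson overstates it by 1/(1 − p). That factor is small when p is low and extreme when p is near 1, which is where SVR is expected to lie. With no comparator arm and hardly any failures, a regression also has nothing useful to estimate. At stake is whether the trial's only measure of cure is reported with limits that make sense.

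The forecast is a second, separate problem. It reads as a minimum and takes for granted that V11 results are complete, which is one of the things this pilot sets out to learn. Because the denominator is not stated, the same data could also be reported as two quite different percentages.

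**Working it through.** **Inputs.** N = 30 (Sample Size); assumed SVR12 98% (Analysis of SVR12); 618/624 (Table 2); 264/277 for genotype 3 (Table 3), a genotype that the inclusion criteria admit; maximum loss 10% (Participant Accrual and Retention).

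**1. The plan's figure.** 30 × 0.98 = 29.4. Pooling the two tables gives 882/901 = 97.9%, and 30 × 0.979 = 29.4. So 29 reproduces, but as an expected count rounded down.

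**2. Chance of at least 29 of 30, all assessed.** P(X ≥ 29) = p³⁰ + 30(1 − p)p²⁹.
- p = 0.98: 0.545 + 0.334 = 0.879, or 88%.
- p = 264/277 = 0.953: 0.586, or 59%.
- p = 618/624 = 0.990: 0.966, or 97%.

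**3. Poisson standard error at 29/30.** Model-based SE of the log rate = 1/√29 = 0.186. Robust SE = √[(1 − p)/(np)] = √[(1/30)/29] = 0.034. Ratio = 1/√(1 − p) = √30 = 5.5. At 27/30 the ratio is √10 = 3.2.

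**4. 95% intervals.**

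| Method | 29/30 | 30/30 |
|---|---|---|
| Poisson, model-based | 67.2% to 139.1% | 69.9% to 143.0% |
| Poisson, robust (log scale) | 90.5% to 103.3% | SE = 0, no interval |
| Exact (Clopper-Pearson) | 82.8% to 99.9% | 88.4% to 100% |
| Wilson | 83.3% to 99.4% | 88.6% to 100% |

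At 29/30 the model-based Poisson interval spans 139.1 − 67.2 = 71.9 points, against 99.9 − 82.8 = 17.1 for the exact interval. A simple Wald interval for the proportion also passes 100% (90.2% to 103.1%), so the promised interval needs a named method. At a true 98% with all assessed, 30/30 has probability 0.98³⁰ = 55%, so the case in which robust variance breaks down is the likeliest single result.

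**5. Information for covariates.** Expected failures = 30 × 0.02 = 0.6, and the chance of at most one is 88%. Any covariate estimate would rest on one woman or none.

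**6. Ceiling case for loss.** If the full 10% were lost before V11, 30 × 0.90 = 27 women would be assessed and 27 × 0.98 = 26.5 documented SVR12 would be expected. Taking 26:
- missing counted as not documented: 26/30 = 86.7% (exact 69.3% to 96.2%);
- assessed women only: 26/27 = 96.3% (exact 81.0% to 99.9%).

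**The case against.** **Poisson regression is not wrong for binary data as such.** With robust variance it is an accepted route to risk ratios, and it removes the 5.5-fold inflation. This stands in general. Here, robust variance and a risk-ratio aim are both unstated, and the robust version still passes 100% at 29/30 and fails at 30/30.

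**The plan already promises intervals for proportions.** A reader might infer that the trial's SVR result must carry limits near 139%. The documents do not support that. The plan prints no SVR interval, and an exact or Wilson interval under the general promise would be sound. The harm is limited to the Poisson output, but the plan leaves two analyses of one result with no stated priority.

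**The 10% is a ceiling.** A reader might infer that about 26 of 30 is the realistic forecast, or that 29 of 30 is impossible. Neither follows. The figure is a maximum to be targeted over the entire study, which runs to 18 months after treatment starts, whereas V11 falls at 6 months. A lost woman may still have SVR, so 29 is out of reach only at the full ceiling with missing results counted as failures, and the plan states no such rule. Visit windows are targets, so a late V11 remains possible.

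**Stopping medication is not loss.** One discontinuation criterion is "Participant is unable or unwilling to comply with required study procedures", from which a reader might infer missing results. The plan asks women who stop medication to complete their remaining visits, and promises reasonable efforts to follow those who withdraw. What stands is that no rule says how a woman without a V11 result is counted.

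**Little turns on SVR12.** With no success threshold, test or stopping rule attached to it, a reader cannot conclude that 26 documented responses would be judged a shortfall. This bears on severity. It does not repair the model or the forecast.

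**Conclusion.** The point holds, at moderate severity; it is not something that must be fixed before the trial can proceed. The Poisson model does not suit this outcome and is not specified well enough to be run sensibly. At the plan's own forecast its model-based standard error is 5.5 times too large and its upper limit is about 139%; the robust form is also unsatisfactory at the results most likely to occur. This matters only where the Poisson result is reported.

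The forecast presents 29.4 as a floor. With all 30 assessed, at least 29 has an 88% chance at a true 98% and about 59% at the Table 3 genotype 3 rate. These figures assume independent women with a common SVR probability; the trial's genotype mix is not given. The 26 of 30 figure also assumes that all 30 take at least one dose and that loss before V11 reaches the 10% ceiling. It illustrates the ceiling case and is not a central forecast. The sample size is unaffected.

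**What to change.** - Delete the Poisson sentence for SVR.
- Report SVR12 as n/N with an exact (or Wilson) 95% interval, and name the method.
- Take as denominator all women who took at least one dose. Count a missing V11 result as SVR not documented, and give the observed-case proportion alongside, since some women without a result may be cured.
- Keep the summaries by race, age, parity, income and insurance descriptive for SVR.
- Restate the forecast: about 29 of 30 expected if all are assessed, with an 88% chance of at least 29 at a true 98% and about 59% at the Table 3 genotype 3 rate. Add, labelled as the ceiling case, that 10% loss before V11 would give about 26 documented SVR12 of 30 (exact 95% interval 69% to 96%).

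The cost is a few lines of analysis text and a less favourable stated forecast. No visit, procedure or sample size changes.
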